The participants are randomly assigned to two experimental groups based on a randomized trial design: two weeks of habitual dietary intake (control period), two weeks of LAB fermented foods, or two weeks of unfermented foods.

The control period is from zero to 14 days, and after these two weeks, baseline data will be collected from all subjects. The second intervention period lasts from day 14 to day 28 (Fig. 1), during which participants will be instructed to consume 100 g of either fermented or unfermented legumes every day, seven days a week, for two weeks.

[figure not shown]

Fig. 1: Trial design

Study population

Healthy adults are recruited from the University College Absalon or the University of Copenhagen canteens from two locations: University College Absalon in Slagelse, Denmark, and University of Copenhagen in Frederiksberg, Denmark.

Inclusion criteria:

- Adults, 18 – 60 years.
- No diabetes.
- Biological sex includes both males and females.

Exclusion criteria:

- Treatment with antibiotics within the last three months.
- Ongoing treatment with non-steroidal anti-inflammatory drugs.
- Metabolic diseases, including diabetes.
- Inflammatory bowel disease (IBD), such as Crohn's disease or ulcerative colitis.
- Allergies or intolerance to legumes.
- People that report eating > 25 g per day of legumes as part of their habitual diet.

Sample size calculation:

Initially, the power calculation is performed by a parallel two-armed comparison of the change in continuous blood glucose levels from baseline (control period). A total of **50 participants (25 participants in each group)** should be recruited to be able to detect a clinically relevant difference of approximately 9 mg/dL in fasting blood glucose (American Dietetic Association (ADA) 2024) between the groups adjusted (fermented vs. unfermented legumes) (18,23–25), assuming a standard deviation of approximately 10-11 mg/dl, a power of 0.8, and a significance level of 0.05, and includes a 10% dropout adjustment. There will be a running inclusion from September 2026.

Control period

All participants are instructed to adhere to their habitual diet during the 14-day control period.

Intervention period

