Participants in the treatment groups are given two weeks of LAB-fermented or unfermented foods, containing 100 g of legumes, including fava beans, peas, and lentils. Fermented and unfermented legumes will be provided and packed as standardized food items to their habitual meals e.g. as hummus, or pasta with legume flour, adding up to 100 g of legumes per day, seven days a week, for two weeks. These test foods can be eaten throughout the day; however, intake of other legumes, except those included in the foods, should be avoided. If participants eat other legumes, this should be noted and accounted for in data analysis. If participants do not consume the full 100 g of legumes, they must weigh the leftovers and take a photo of the remaining food and report to the researchers.

Primary outcome:

Continuous Glucose Monitoring

Continuous Glucose Monitoring (CGM) will be measured in real-time and intermittently scanned CGM (isCGM) bi-weekly with an isCGM sensor (model Abbott Freestyle Libre PRO). This method is a minimally invasive method, as the sensor is placed on the participant's arm (26–30), by participants themselves after careful instructions, incl. videos. The Abbott Freestyle Libre PRO is blinded to the participants to avoid habitual changes, and it measures CGM in real-time throughout the entire 14-day period. The study follows the Standardized CGM metrics for Clinical Care, and the 14-day duration is aligned with the international recommendations (26,30). To ensure accurate and meaningful interpretation of CGM, adequate glucose data is collected according to the recommendation (70% of data from 14 days) (26,30). Data from participants with a CGM activity < 70% will be analyzed with the intention to treat principles.

Secondary Outcomes

The secondary outcome includes changes in inflammation, cholesterol, long-term blood glucose levels, systolic and diastolic blood pressure, body composition, the fecal microbiomes and metabolome, and dietary intake. Digestive abnormalities will also be assessed.

Inflammation monitoring

Fasting C-reactive proteins (CRP) monitoring will be measured at baseline, 14 days, and at day 28 by a finger prick test using a QuickRead go PLUS Instrument (#154580-4).

Cholesterol monitoring

Fasting cholesterol monitoring will be conducted at baseline, 14 days, and at day 28 by a finger prick test using a QuickRead go PLUS Instrument (#154580-4).

Long-term blood glucose monitoring

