For ¹H NMR spectral data, fecal metabolites are assigned, and their concentrations are quantified using the Chenomx software. Subsequently, statistical analysis will be conducted on the individual metabolites as continuous variables are described above.

5. Risks, side effects, and disadvantages in the short and long term

In the study, no serious adverse events or risks are expected. There are no known serious adverse effects associated with the consumption of either non-fermented or fermented legumes in healthy adults, and the official dietary guidelines recommend an intake of 100 g of cooked legumes per day. All participants participate voluntarily and can withdraw from the study at any time. All participants are informed about the product content, and potential participants with food allergies or intolerances are excluded before starting the study.

The finger-prick test is a simple and nearly painless tool to measure inflammation, cholesterol, and blood glucose. No blood is collected, and the test is performed by trained researchers. A disinfectant is used to reduce the already small risk of bleeding, bruising, or infection.

Stool samples is safe to collect when EasySampler is used. Only a small sample is needed (approximately 10 g). There is no health risk when following the instructions.

This project meets the guidelines of the Declaration of Helsinki II, as well as the guidelines of the Regional Ethics Committee.

SJ-1132-120770, Version 3, 16-02-2026

The study has been submitted to the Science Ethics Committees for Region Zealand
j.nr.: SJ-1132-120770.

The study is covered by the Danish Patient Compensation scheme (In Danish: Patienterstatningen)

6. Biological material is collected.

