Recruitment of project participants takes place from the Absalon or the UCPH canteens. The first step in recruitment involves the principal investigator writing to inform all campus employees and students about the project's purpose, content, and course. Posters are displayed to inform people about the project. In the next step, oral information in the canteens is provided by the principal investigator and students. Participant information (written information) is provided as well as the leaflets "Subjects' rights in a health science research project", and "Before you decide - to be in health science experiments". The written information contains a description of the project, its purpose, method, and possible disadvantages associated with the participants' participation. Participants will receive both verbal and written information by email and will have 24 hours to decide before signing the consent form. There will be an information meeting where participants can ask questions, and they may bring a support person if needed. The meeting will be held individually according to participants' needs—by phone, online, or as an in-person meeting in a private, undisturbed room. Participation in the project is voluntary, and the participants have the opportunity, without further justification, to interrupt the collaboration and their participation in the project. In the third step, the residents then have 24 hours to decide whether they want to participate in the project and sign a declaration of consent. The content is obtained at day 1 (baseline). There is a running inclusion. During the project period, the participants can obtain further information about the project from the principal investigator. Participants have the opportunity to withdraw consent at any time during the project.

12. Publication of results

Based on the project's results, it is expected that two scientific publications will be submitted.

Table 2: Expected publications

Title proposal	Scientific journals proposal
Implementing a high-legume diet in everyday meals: a feasibility study of 100 g/day legume consumption in Denmark	Nutrients
Health effects of introducing locally sourced legumes into regular Danish diet: A parallel trial comparing fermented and unfermented legumes	Frontiers in Nutrition

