The results obtained will be published in anonymous form in international scientific journals and may be presented at conferences. Positive, negative, and inconclusive results will be published. If, contrary to expectations, the results are not published in a scientific journal, they will be published on www.clinicaltrials.gov and www.clinicaltrialsregister.eu

13. Ethics In the study, no serious adverse events or risks are expected. There are no known serious adverse effects associated with the consumption of either non-fermented or fermented legumes in healthy adults. All participants are informed about the product content, and potential participants with food allergies or intolerances are excluded before enrollment. . This project meets the guidelines of the Declaration of Helsinki II, as well as the guidelines of the Regional Ethics

SJ-1132-120770, Version 3, 16-02-2026

Committee. The research project has been submitted to the Science Ethics Committees for Region Zealand j.nr.:SJ-1132-120770.

a. Why the therapeutic benefit for the subjects or future patients justifies the studies

Danish pulses is a project aimed at getting more Danish-grown legumes—such as beans, peas, and lentils—into the food we eat daily. Legumes have a distinctive composition of proteins, – which can replace some of the meat in a meal, dietary fiber, which supports digestion and provides longer-lasting satiety, and carbohydrates. This combination makes legumes particularly interesting from a health perspective. The fiber and protein content may help slow the rise in blood sugar after a meal and contribute to satiety for a longer time.

The project covers the entire “journey” of legumes—from field to plate—and works with several different species and varieties. The knowledge generated from the study may therefore be relevant to many Danes and support a greener future.

[figure not shown]
13. Information regarding compensation

See. Pkt. 10.

Timeline perspective

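### The eligibility list excludes only legume allergy or intolerance, while the risk and ethics sections promise exclusion for food allergies and intolerances in general

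*Protocol*

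**What the plan says.** Protocol section 3, Study population, lists six exclusion criteria: recent antibiotics, ongoing anti-inflammatory drugs, metabolic disease, inflammatory bowel disease, a food-reaction item, and high habitual legume intake. The food-reaction item reads "Allergies or intolerance to legumes". None of the three inclusion criteria concerns food reactions.

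Two later sections describe the exclusion more widely:

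- Section 5 (Risks): "All participants are informed about the product content, and potential participants with food allergies or intolerances are excluded before starting the study".
- Section 13 (Ethics): "All participants are informed about the product content, and potential participants with food allergies or intolerances are excluded before enrollment".

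Section 3, Intervention period, says the legumes are "packed as standardized food items to their habitual meals e.g. as hummus, or pasta with legume flour". No ingredient list is given.

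Section 11 (Recruitment and informed consent) describes the information given before consent: "Participants will receive both verbal and written information by email and will have 24 hours to decide before signing the consent form". It also provides for a meeting at which questions can be asked.

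**The concern.** The list that decides who may enter the trial is narrower than the protection described in the safety and ethics sections. For a volunteer whose allergy or intolerance is to something other than legumes, the answer depends on which section the staff apply. If they work from the criteria list, as is usual, the narrower rule applies.

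This is a matter of participant safety and of what the ethics committee is told. In both sections the allergy exclusion stands in the same paragraph as the expectation of no serious adverse events. A reader of those paragraphs would assume a protection that the list does not fully provide. For a reaction to a non-legume ingredient, the remaining safeguard is that the volunteer notices the ingredient in the product information and declines.

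**Working it through.** No formula applies to the main point; it is a comparison of texts in the current version of one document.

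| Place in the protocol | Scope of the food-reaction exclusion |
|---|---|
| Section 3, Exclusion criteria | Legumes only |
| Section 5, Risks | Food in general, no restriction |
| Section 13, Ethics | Food in general, no restriction |

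**Step 1: is there a conflict?** Take a volunteer with an allergy to some food other than a legume who meets every other criterion. Under section 3 this person is eligible. Under sections 5 and 13, read literally, this person is excluded. Both cannot hold.

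**Step 2: does the difference bear on the intervention?** It would not if the test foods were legumes and nothing else. The examples in the Intervention period text are prepared foods, so other ingredients are plausible. The protocol names none, and the argument does not depend on any particular allergen.

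**Step 3: does any reading reconcile the sections without an edit?**

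- If the general phrase is shorthand for legume allergy, sections 5 and 13 overstate the protection and need correcting.
- If it means allergies relevant to the products supplied, the intended rule is wider than legumes and the list in section 3 is too narrow.
- If it means any food allergy at all, the list is again too narrow.

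Each reading requires a change somewhere.

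**Step 4: how much exposure is involved?** The inputs are in section 3: 100 g of legumes per day, 14 days, 50 participants.

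- Per participant: 14 days × 100 g/day = 1,400 g of legumes, plus an unstated amount of other ingredients.
- Whole trial: 50 × 14 days = 700 participant-days. This is a maximum, because the 50 already allows for 10% dropout.

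These figures describe how much test food is eaten. They are not an estimate of how many people would react.

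**The case against.** The strongest reply is that the protocol should be read as a whole. Sections 5 and 13 state twice that such people are excluded, so the wider rule is already there. Both statements complete a sentence that begins "All participants are informed about the product content", so the natural meaning is allergies relevant to the products, with section 3 naming only the main one. This is a fair reading and may well be what was intended. It does not remove the problem: on that reading the criteria list is narrower than the intended rule, and the list is what staff would normally use to screen.

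Several further points stand and limit the weight of the finding:

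- No non-legume allergen is shown to be in the foods; its presence is an assumption.
- Section 11 describes no check against ingredients, but it describes no check against any other criterion either. Its silence is weak evidence that an ingredient check is absent.
- Volunteers learn the product content, receive verbal and written information, have 24 hours to decide and may withdraw at any time. This lowers the risk, although information is not an eligibility rule.
- Section 5 rests its safety expectation mainly on the absence of known serious effects of legumes in healthy adults and on official intake guidance. The allergy exclusion is at most one supporting point.

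The issue cannot be left to a statistical analysis plan, because eligibility criteria belong in the protocol.

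**Conclusion.** The concern holds. As written, section 3 excludes reactions to legumes only, while sections 5 and 13 state a general exclusion, and no reading makes all three correct without an edit. The textual conflict is certain. The safety consequence is conditional: it requires that a test food contains a non-legume ingredient to which some volunteer reacts, and that this volunteer neither declines nor is screened out. The protocol gives no figure from which to estimate how often that would happen. Randomisation, outcomes, sample size and analysis are not affected. The point should be fixed because it concerns participant protection and the repair is small.

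**What to change.** Reword the criterion in section 3 to: allergy or intolerance to legumes or to any other ingredient of the test foods. Use the same wording in sections 5 and 13. Before enrolment, screen each volunteer against the actual ingredient list of every test food in both arms. Keep the disclosure of product content as an additional safeguard.

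The cost is one line in the exclusion list, matching wording in two sections and one screening question; a few volunteers may be screened out. This version is dated 16-02-2026 and inclusion is planned from September 2026, so by these dates the change can be made before anyone is enrolled.

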including a thorough written introduction(33,34). Fecal pH will be determined by mixing fecal matter 1:2 with sterile MilliQ-water after which pH is measured. Total fecal DNA will be extracted using standard methods. The gut microbial metagenome will be determined by shotgun high-throughput sequencing using long-read Oxford Nanopore-based sequencing(33,34). Before any further bioinformatics processing the raw reads will be purged of any human DNA-related sequences.. Fecal short chain fatty acids (SCFA) and other fecal metabolite concentrations, incl. free amino acids, are determined using high-field nuclear magnetic resonance NMR (34) on fecal samples..

Dietary intake

Data on dietary intake will be collected by three-day dietary records with photos to evaluate adherence to the intervention. The dietary records will be collected once during the control period and once during the intervention period. Photos will be used for main meals and leftovers of legumes.

Physical activity will also be documented as part of the dietary records and used to estimate energy expenditure. Furthermore, data on dietary intake will be used to assess compliance with the intervention.

Digestive abnormalities

Digestive abnormalities are identified through IBS symptoms and will be assessed using self-reported questionnaires at baseline, follow-up 1, and 2, using the IBS Severity Scoring System (IBS-SSS) for assessment of the following symptoms: abdominal distension, abdominal pain, satisfaction with bowel habits, and the extent to which symptoms affect the quality of life (QoL) (35).

Overall data collection

Table 1: Data collection

Variables	Methods	Baseline Day 0	Follow-up 1 Day 14	Follow-up 2 Day 28
Age		x		
Sex		x		
Bio markers				
Blood glucose	Continuous blood glucose levels by glucometer: Abbott Freestyle Libre PRO	x	x	x
Cholesterol levels	Prick-test	x	x	x
C-reactive protein	Prick test	x	x	x
Long-term blood glucose	Prick test	x	x	x
Blood pressure	Systolic and diastolic blood pressures	x	x	x
Body composition				
Body composition incl. body weight, kg	Body Impedance Analytics (BIA)	x	x	x
Fat mass (FM), kg		x	x	x
Fat free mass (FFM), kg		x	x	x
Height, meters	Dynamometer	x		
Body Mass Index (BMI)	BMI is calculated by dividing weight (kg) by height (m) squared (kg/m ²).	x	x	x

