Waist and hip circumference (Waist/hip ratio), cm	Waist circumference was measured at the midpoint between the lowest rib and the upper part of the iliac bone in a standing position. Hip circumference was measured at the site of the largest circumference between the waist and thighs.	x	x	x
Gut microbiome and metabolites				
Gut microbiome composition	Near-full length 16S rRNA gene amplicon sequencing	x	x	x
Short chain fatty acids (SCFA) and other metabolites	¹ H NMR spectroscopy	x	x	x
Other variables				
Dietary intake	Three days' dietary records with photos	x		x
Digestive abnormalities	IBS Severity Scoring System questionnaire	x	x	x

4. Statistical analysis

Stages of data processing will begin with descriptive analyses of variables secondary to outcomes for all participants at baseline. These characteristics will be tested using analysis of covariance (ANCOVA) when the data are normally distributed, and the Mann–Whitney U test when the data are not normally distributed. Comparisons of the incremental area under the curve (AUC) in the control (baseline) period will be performed against the two groups (group 1 and group 2), and differences between groups will also be assessed.

Continuous variables will be presented as the mean and 95% confidence interval (CI) in the format [lower limit, upper limit] when the data are normally distributed. Differences between continuous variables will be tested using ANCOVA. Categorical variables will be presented as percentages (e.g., sex), and differences will be tested using Fisher's exact test to compare groups (group 1 and group 2). A P-value < 0.05 will be considered statistically significant. Statistical analyses will be conducted using a statistical software program for scientific research, such as R (RStudio; © 2009–2023 Posit Software, PBC).

For 16S rRNA gene amplicon sequencing data, raw FASTQ data will be subjected to second-level demultiplexing, quality filtering, and amplicon sequence variant (ASV) definition, as well as taxonomy assignment, using the in-house established LACA pipeline (<https://github.com/yanhui09/laca>). Subsequently, the effects of the intervention on alpha- and beta-diversity metrics, compositional changes, and correlations with anthropometrics, metabolites, and intervention arm will be evaluated as previously described (34,36).

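### The power statement, the primary outcome and the analysis section use different glucose variables, so the 80% power is not shown for any metric the trial will analyse

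*Protocol*

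**What the plan says.** **Section 3, Sample size calculation.** The calculation is introduced as a "parallel two-armed comparison of the change in continuous blood glucose levels from baseline (control period"). The effect is then set on another variable: 25 participants per arm should suffice to "detect a clinically relevant difference of approximately 9 mg/dL in fasting blood glucose", "assuming a standard deviation of approximately 10-11 mg/dl", with "a power of 0.8, and a significance level of 0.05"; the total "includes a 10% dropout adjustment". The text does not say whether the SD belongs to fasting glucose, to its change or to a CGM metric.

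**Section 3, Primary outcome.** The outcome is CGM. Of the sensor it is said that "it measures CGM in real-time throughout the entire 14-day period". The text refers to the standardised CGM metrics as a group and selects none.

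**Section 3, Table 1.** Blood glucose is listed by CGM only. The finger-prick rows are cholesterol, CRP and long-term glucose (HbA1c). There is no separate fasting glucose row.

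**Section 4, Statistical analysis.** The one curve comparison named is: "Comparisons of the incremental area under the curve (AUC) in the control (baseline) period will be performed against the two groups", with differences between the groups also assessed. No reference level or time window is given. A general sentence adds that continuous variables are compared by ANCOVA, without naming a glucose variable.

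**The concern.** A power statement is informative only if its effect size and SD belong to the variable tested. Here the effect size comes from fasting glucose, the primary outcome is a 14-day recording with no summary measure, and the analysis section names a derived area. These are not interchangeable. Fasting glucose is a level. Incremental AUC, in its usual form, measures the rise above a starting level and removes that level.

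Two things are at stake. The 80% power may not apply to the primary test. And a true lowering of glucose of the size planned for could, under one common definition of the analysis variable, leave the result unchanged.

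**Working it through.** **1. Reproducing N = 50.** Inputs from the Sample size calculation: difference 9 mg/dL, SD 10-11, power 0.80, alpha 0.05, 10% dropout. Two-sided testing is assumed, as sidedness is not stated.

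n per arm = 2 × (1.960 + 0.842)² × (SD/9)², rounded up, then divided by 0.90 and rounded up.

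| SD (mg/dL) | n per arm | after dropout | total |
|---|---|---|---|
| 10 | 20 | 23 | 46 |
| 10.5 | 22 | 25 | 50 |
| 11 | 24 | 27 | 54 |

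The stated 50 is matched at the middle of the stated SD range. One-sided testing gives only 18 to 22 per arm after dropout, so two-sided is the matching reading.

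**2. What the power refers to.** With 22 completers per arm, power ≈ Φ(9 / (SD × √(2/22)) − 1.960). At SD 10.5 this is Φ(9/3.166 − 1.960) = Φ(0.883) = 0.81; at SD 10 and 11 it is 0.85 and 0.77. These values hold for a 9 mg/dL difference in a variable with that SD, which the paragraph identifies as fasting glucose.

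**3. If the analysed variable carries only part of the fasting effect.** Assume a mean-glucose metric with the same SD of 10.5 that shows 75%, 50% or 25% of the 9 mg/dL. The same formula gives power of about 0.57, 0.30 or 0.11. The fractions are assumptions; the protocol gives none.

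**4. Incremental AUC under two definitions.** Take an assumed 2-hour curve sampled every 15 minutes: 90, 105, 125, 130, 122, 112, 104, 97, 92 mg/dL.

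- Total area (trapezoid): 15 × (977 − 91) = 13,290 mg/dL·min. Above its own start: 13,290 − 90 × 120 = 2,490.
- Whole curve lowered by 9: total 13,290 − 9 × 120 = 12,210. Above its own start, now 81: 12,210 − 81 × 120 = 2,490. The difference is zero.
- Same lowered curve against a fixed control-period level of 90: 12,210 − 90 × 120 = 1,410. The fall shows.
- Only the starting value lowered by 9: incremental area rises to about 3,503, the opposite direction.

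The zero under the first definition does not depend on the curve chosen, because a constant shift cancels. A test of a variable with no true difference rejects at the alpha level, 0.05. Mean glucose would fall by the full 9 mg/dL, and total AUC by 9 × 24 = 216 mg·h/dL per day.

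**5. Detectable difference for a CGM metric.** Evaluable per arm: 25 × 0.90 = 22.5. Normal approximation: 2.802 × √(2/22.5) = 0.835 SD; the t distribution raises this to 0.8545 SD. The documents give no SD for any CGM metric. At assumed SDs of 5, 8 and 11 mg/dL the detectable difference is 4.3, 6.8 and 9.4 mg/dL.

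**The case against.** **The power paragraph does name continuous glucose.** It does, so it is not simply a fasting-glucose calculation. It names one variable and takes its figure from another, and the inconsistency lies within the paragraph as well as between sections.

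**A reader might infer that incremental AUC is the only planned primary analysis, or that the effect is bound to vanish from it.** The protocol does not support either. The AUC sentence names neither CGM nor the primary outcome; linking it to CGM is an inference, though no other listed outcome fits. The general ANCOVA sentence could cover a mean or fasting sensor value. With a fixed control-period reference a uniform fall would show.

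**A reader might infer that meal start times are indispensable and mostly missing**, since "The dietary records will be collected once during the control period and once during the intervention period" and each covers three days. That applies only to post-meal AUC, and section 4 does not say post-meal.

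**Fasting values may be obtainable.** The sensor runs day and night, so a window could be extracted. Section 5 mentions blood glucose among the finger-prick tests, but Table 1 shows only HbA1c there.

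**A SAP may select the metric.** It may, so one cannot conclude that the choice will follow sight of the data. But a SAP that selects one of these variables would still disagree with another part of the protocol.

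**The CGM figures in step 5 do not show a loss of power.** Correct: two of the three detectable differences are below 9 mg/dL. They show only that the 9 mg/dL figure is unverified for a CGM metric.

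**Incremental AUC has a rationale.** Section 13a refers to a slower rise in blood sugar after meals. That supports keeping the measure, provided it is defined.

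**Conclusion.** The point stands as a contradiction within the protocol. The sample size arithmetic is sound: 50 follows from the stated inputs at SD 10.5. The 80% power is established only for a 9 mg/dL difference in fasting glucose, which is neither a listed outcome nor a named analysis variable. It is not established for incremental AUC or for any other CGM metric.

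The size of the consequence depends on a definition the protocol does not give. With incremental AUC above each curve's own start, power against a uniform shift is 5%. With a fixed control-period reference the shift is visible, but its power is unknown because no SD or effect size is given. The partial-effect powers (0.57, 0.30, 0.11) and the CGM SDs rest on assumed values. Because the mismatch reaches the primary outcome, its power and its test together, it should be resolved before inclusion begins in September 2026.

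**What to change.** Make the power statement, the primary outcome and the primary analysis refer to one defined CGM metric, with its window. Two workable choices are:

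- mean sensor glucose over days 14-28; or
- the mean over a fixed overnight fasting window, which keeps the link to the 9 mg/dL figure.

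Compare the arms by ANCOVA with the same metric from days 0-14 as covariate. Restate the detectable difference for that metric (about 0.85 SD with 22.5 evaluable per arm), giving the source of the SD or a stated range, and say whether it is the SD of the raw value, of the change or of the covariate-adjusted residual.

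Keep incremental AUC as a secondary measure with a stated reference level and window. Keep the comparison with the control period as a separate analysis, since the section 2 glucose hypothesis is about legumes against habitual diet and the between-arm ANCOVA does not test it.

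Cost: protocol wording and a recalculated power statement, with no added visits, samples or devices. An SD for the chosen metric must be found or assumed, and post-meal excursions are no longer the lead measure.
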